Appendix B: Case Report Forms

These are sample case report form drafts for the study “Psilocybin-assisted psychotherapy in the management of anxiety associated with stage IV melanoma.”

The series of case report forms represents CRFs for the first six visits of the study. The second half of the study, consisting of visits seven through 10, will record identical or nearly identical information as presented in the first six visits.

CONTAINS

SCREENING (Visit #1-#2)
BASELINE EVALUATION (Visit #3)
INTRODUCTORY PSYCHOLOGY SESSIONS (Visits #4-#4.5)
EXPERIMENTAL (PSILOCYBIN-ASSISTED)
PSYCHOTHERAPY SESSIONS (Visit #5)
INTEGRATIVE PSYCHOTHERAPY (Visit #6)
DAILY PAIN ASSESSMENT (Visits #3-#10)
PAIN DIARY (Visits #3-#10)
MEDICATION DIARY (Visits #3-#10)
MEDICATIONS AND ADVERSE EVENTS (Visits #2-#10)

Baseline - Psychiatric Evaluation:

Please write in the score or scores for each outcome measure. All scale scores must be complete.

Baseline Measures:

Date of Administration ____ - ____ - ____
dd mm yy

Anxiety, Depression, Hopelessness and Thoughts on Hastened Death

Scale	Score
STAI	
State	
Trait	
Total	
HADS	
Anxiety	
Depression	
Hamilton Anxiety Rating Scale (HAM-A)	
Total	
Hamilton Depression Rating Scale (HAM-D)	
Total	
KPRS	
Total	

Baseline – SCID

Date of Evaluation ____ -

____ - ____

dd

mmm yy

DSM-IV Diagnosis	Yes	No	Comment
PTSD			
Major Depression			
Panic Disorder			
Generalized Anxiety Disorder			
Anxiety Disorder 2° to General Medical Condition SPECIFY MEDICAL Condition:			
Bipolar Affective Disorder-1			
Bipolar Affective Disorder-II			
Dissociative Identity Disorder			
Psychosis			
Eating Disorder			
Personality Disorder SPECIFY D/O:			
Substance Abuse or dependence (60 days)			
Other DSM IV diagnosis-1 Specify:			
Other DSM IV diagnosis-2 Specify:			

Any Axis 1 diagnosis?

Yes No

Any Axis 2 diagnosis?

Yes No

Baseline - Measures (continued)

Date of Administration ____ -

____ - ____

dd

mmm, yy

Quality of Life and Everyday Life Functioning

Please fill in the appropriate scale or total scale scores for each scale listed below.

Scale	Score
EORTC-QLQ-30	
Physical	
Role	
Emotional	
Social	
Cognitive	
Fatigue	
Pain	
Nausea/vomiting	
Global	
FACIT-Sp[^]	
Sense of Meaning and Peace	
Role of Faith	
Total	
Mini-Mental State Exam	
Total	
Self-Expansiveness Level Form	
Personal	
Middle	
Transpersonal	
Total	

Urine Drug Screen

Positive PECIFY: _____
 Negative

ARE POSITIVE RESULTS ONLY DUE TO CURRENT MEDICATIONS: YES NO

Past Substance Use

Previous Alcohol Abuse/dependence yes no # of prior treatments _____

In the last 60 days yes no

Previous Drug Abuse/dependence yes no # of prior treatments _____

In the last 60 days yes no

Baseline - General Well Being

	Visit Date dd-mmm-yy	Subject Demeanor and State of Mind enter code	Notes
Visit 2			

- 1= Very stable and calm
- 2= Stable and calm
- 3= Slightly stable and calm
- 4= Slightly distressed
- 5= Distressed
- 6= Very distressed

Baseline – Subject Enrollment Decision:

After reviewing all screening and baseline source data, and all inclusion/exclusion criteria does the principal investigator conclude that the subject has met all study criteria?

Yes No

If the answer above is “No” please explain:

If “Yes” Date of enrollment ____ - ____ - ____
 dd mmm yy

Assigned Subject Number ____ ____ ____

PI signature _____

Therapy and Evaluation 1:

Please write in the score or scores for each outcome measure. All scale scores must be complete.

Visit 4 **Date of Administration** ____ - ____ - ____
 dd mmm yy

Anxiety, Depression, Hopelessness and Thoughts on Hastened Death

Scale	Visit 4	Visit 4.5	Visit 5	Visit 6
STAI				
State				
Trait				
Total				
HADS				
Anxiety				
Depression				
MMSE				
Total				
KPRS				
Total				

Scale	Visit 4	Visit 4.5	Visit 5	Visit 6
EORTC-QLQ-30				
Physical				
Role				
Emotional				
Social				
Cognitive				
Fatigue				
Pain				
Nausea/vomiting				
Global				
FACIT-Sp[^]				
Sense of Meaning and Peace				
Role of Faith				
Total				
Mini-Mental State Exam				
Total				
Self-Expansiveness Level Form				
Personal				
Middle				
Transpersonal				
Total				

Visit 4-6 - General Well Being:

	Visit Date dd-mmm-yy	Subject Demeanor and State of Mind enter code (1 - 6)	Since last time seen the subject has enter code (A - C)	Risk of Suicidality enter code (X - Z)	Notes
Visit 4					
Visit 4.5					
Visit 5					
Visit 6					

1= Very stable and calm
 2= Stable and calm
 3= Slightly stable and calm
 4= Slightly distressed
 5= Distressed
 6= Very distressed

A= Worsened.
B= Remained pretty much the same.
C= Improved.

X = No risk of suicide
Y = Some risk of suicide
Z = Risk of suicide

Visit 5 - Experimental Session # 1: Inclusion/Exclusion

Review of Inclusion and Exclusion Criteria

Urine Pregnancy Test

- Positive
- Negative
- Not Applicable (Subject is Male, Non-child bearing potential)

Urine Drug Screen

- Positive : List positive results: _____
- Negative

Liver Function Results	
------------------------	--

Are positive results due to participant's medications? Yes No N/A

Does subject continue to **meet all inclusion and no exclusion criteria**? Yes No

If no, specify: _____

Visit 5 - Experimental Session # 1: Administration

Record time of initial IP administration ____:____ AM / PM

Record Bottle number of Investigational Product _____

Visit 5 - Physiological measures and Body temperature:

Please record maximum and average figures for each measure, and time of measurement for maximum increase. Body temperature should be recorded in degrees Centigrade.

	Average baseline	Maximum Change in Value	Time Max Change Recorded	Post-Drug average
Systolic Blood Pressure (mm/HG)				
Diastolic Blood Pressure (mm/Hg)				
Pulse (BPM)				

Was blood pressure ever above 160/110? Yes No

If "Yes," for how long was blood pressure higher than 160/110? _____ h _____ min.

If the duration of elevated blood pressure was less than 1 hour, write time in minutes only and write "0" (zero) in "hours."

Visits 5-6 Spontaneously Reported Side-Effects:

Please record the maximum intensity of any spontaneously reported effects up to 24 hours after drug administration.

Visit	Visit 5 Experimental Session #1		Visit 6 24 hrs post
	Duration in hours	Intensity	Intensity
Report Max Intensity for the 24 hour period 0= None Reported 1= Mild 2= Moderate 3= Severe	Report Duration to the nearest hour for the first 24 hours only		
Check None if no symptoms are reported for the 1 st 24 hours		 None	 None
Anxiety			
Chills/feeling cold			
Derealization			
Depersonalization			
Difficulty Concentrating			
Dilated pupils			
Emotional Lability			
Feeling hot			
Impaired cognition			
Impaired gait/balance			
Nausea			
Objects/people different			
Parasthesias			
Perspiration			
Simple visual images			
Somatization			
Repetitive thoughts			
Time perception altered			
Unusual thoughts			
Visual illusions			
Weakness			
Other:			

Visit 6 States of Consciousness Questionnaire

Visit 6 (24 hours post-psilocybin session 1)

Please write in the score or scores for each outcome measure. All scale scores must be complete

Scale	Visit 4	Visit 4.5	Visit 5	Visit 6
SCQ				
Internal unity				
External Unity				
Transcendence of Time and Space				
Ineffability and Paradoxicality				
Sense of Sacredness				
Noetic Quality				
deeply Felt Positive Mood				
Total				
SELF				
Personal				
Middle				
Transpersonal				
Total				

NK cell Count

Please write in the NK cell count recorded at this time _____

Subject Number _ _ _ _

CRF

VAAS Month # _____

[name],

Page # _____ of _____

Daily Diary of Pain and Anxiety

Today's Date _____

Your Initials _ _ _

How Anxious did you Feel Today?

No Anxiety	Much Anxiety
-----------------------	-------------------------

Do you want to say anything else about your anxiety? If you do want to say more, please write any additional thoughts or comments below, including any changes in anxiety, type of anxiety, anxiety triggers or responses to being anxious.

How Much Pain did you Feel Today?

No Pain	Much Pain
--------------------	----------------------

Do you want to say anything else about the pain you felt today? Please write in below any additional thoughts or comments about your pain today, including any changes in type or amount of pain, any changes in location of pain, or any changes in your feelings about the pain.

Subject Number _____
 PI: [name]

CRF
 Psychotropic Medication CRF

Visits 1 through Termination
 Page X2 Series _____ √ if last page

Psychotropic Medication and Tapering

Record psychotropic medications previously used **and** psychotropic medications subject is on at visit1. Check the Prestudy box (include start date if known) and provide Disorder Code. Check Tapered box for medications tapered from V1-V3. Provide route, dose and stop date for all medications. Record **all new psychotropic medications** taken after visit 1 through termination visit. Provide route, dose and start date. Provide AE# (from AE page) and check Rescue box if used as a rescue medication or complete Other Reason for Treatment. Check the Continuing box if continuing at study termination. Do not record each instance of a pain management medication unless it is used only intermittently. **CHECK IF NONE**

Medication	Route	Dose	Start Date (dd/mmm/yy)	Stop Date (dd/mmm/yy)	Reason for Treatment Complete at least one column		
					Prestudy Disorder Code#	AE#	Other
			 Prestudy	 Tapered		 Rescue	
			 Prestudy	 Tapered		 Rescue	
			 Prestudy	 Tapered		 Rescue	
			 Prestudy	 Tapered		 Rescue	
			 Prestudy	 Tapered		 Rescue	
			 Prestudy	 Tapered		 Rescue	
			 Prestudy	 Tapered		 Rescue	
			 Prestudy	 Tapered		 Rescue	
			 Prestudy	 Tapered		 Rescue	

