All outcome measures selected for this study were chosen because they are well-recognized in the literature and because they are or will be used in related pilot studies, allowing comparison across these investigations. The primary outcome measure for this study will be the HADS anxiety score. The investigators will also measure anxiety with the STAI and the HAM-A. The investigators will assess depression with HADS depression scores and with the HAM-D. Participant beliefs about life purpose and spirituality will be measured with the FACIT-Sp, spirituality in relation to self-concept by the SELF, and quality of life will be assessed with the EORTC-QLQ-C15. Daily pain levels will be assessed via participant response on a visual analog scale, and daily pain and anxiety medication use will serve as an indirect measure of anxiety and experienced pain. Natural killer cell counts will serve as a measure of innate immune system function.

All participants will be screened via SCID and HADS, as described above in “Screening”. The investigators will also use MMSE scores to assess study eligibility and mental competence throughout the course of the study.

The SCQ will serve as a process measure, assessing presence and degree of effects of psilocybin, and the SELF will serve as a process measure of self-boundary change. The KRPS, a measure frequently employed in studies of people with cancer, will serve as a means of rating performance status.

Table 1: List of assessments for use in this study. Time listed in minutes.

Assessment	Abbreviation	Measure of	Time needed	Clinician rated	Participant Self-rated	Purpose of Assessment/Measure
Daily Medication Diary	--	Anxiolytic & pain management meds	5 min		X	Outcome
Daily Pain Level Diary	--	Daily pain levels	5 min.		X	Outcome
Europ. Organiz. For Research and Treatment of Cancer; Quality of Life Questionnaire-C15	EORTC QLQ-C15	Global quality of life	5-10 minutes.		X	Outcome
Functional Assessment of Chronic Illness Therapy-spirituality	FACIT-Sp	Spiritual or life purpose beliefs	5 min.		X	Outcome
Hamilton Anxiety Rating Scale	HAM-A	Anxiety	5-10 min	X		Outcome
Hamilton Depression Rating Scale	HAM-D	Depression	5-10 min	X		Outcome
Hospital Anxiety and Depression Scale#	HADS	Anxiety + Depression	5-10 min.		X	Screening & Outcome
Karnofsky Performance R__ Scale	KPRS	Everyday life function	5 minutes	X		Supplemental
Mini Mental State Examination	MMSE	Mental status / competency	15 minutes	X		Screening, continued eligibility

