The sponsor or the investigator (following consultation with the sponsor) has the right to discontinue this study at any time. If the trial is prematurely terminated, the investigator is to promptly inform the study subjects and she or he should assure appropriate therapy and follow-up. If the trial or study is prematurely discontinued, all procedures and requirements pertaining to the archiving of the documents will be observed. All other study materials will be returned to the sponsor, will be treated in accordance with federal and local regulations. DEA requires destruction of unused schedule 1 drugs in studies.

Data Analysis

The primary analyses for this study will be a repeated measures analysis of variance (ANOVA) with condition (active placebo versus experimental dose) as a between-subject

factor and time of administration (baseline versus two weeks after the second experimental psilocybin-assisted session) as a repeated measure. The investigators will employ separate repeated measures ANOVAs to examine the effects of psilocybin-assisted psychotherapy on all outcome variables, including the primary outcome variable. Separate analyses will be performed for HADS, HAM-A and STAI anxiety scores, HADS and HAM-D depression scores, EORTC-QLQ-C15 scores, FACIT-Sp scores and NK cell counts. The investigators will perform post-hoc tests (as Tukey's test) on any statistically significant interactions. Probability of rejecting the null hypothesis will be set at 0.05. Because of the pilot nature of this study and small sample size, we will not employ Bonferroni corrections for when examining analyses results for measures of anxiety. In the case of pain levels measured by daily diary, the investigators will perform two repeated measures ANOVAs comparing average pain levels at baseline versus average pain levels for the weeks immediately after the first and after the second experimental sessions, with p. set at 0.05. The investigators are interested in discovering whether there are differences in pain level between active placebo and experimental dose participants immediately after undergoing psilocybin-assisted psychotherapy.

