Appendix A Assessments and Measures

Daily Medication Diary: This is a daily log of all anti-anxiety and pain management medication intended as an indirect measure of changes in anxiety and pain. Each form will also remind participants to contact the investigators prior to initiation of any drug or medication not already reviewed during the intake evaluation. This measure is used in a study of MDMA-assisted psychotherapy in people with advanced stage cancer.

Daily Pain Level Diary: This is a daily self-assessment of participant pain. This is a simple measure that consists of a 10-cm line labeled at one end with "no pain" and at the other end with "worst pain possible." Scoring is accomplished by having the participant mark the line to indicate pain intensity, and the line is then measured to the mark on a 0- to 10-point scale. Extensive prior research indicates that visual analog pain scales are reliable and valid as both a sensitive measure of pain and as a measure of change in pain (Ohnhaus and Adler 1975).

European Organization for Research and Treatment of Cancer Quality of Life Questionnaire-C15: (Groenvold et al. 2006) is the short form of a questionnaire (Aaronson et al. 1993) that currently is one of the most widely accepted measures of quality of life. This instrument has 15 items yielding scores for 5 subscales (physical, role, emotional, social, and cognitive functioning) and 3 symptom subscales (fatigue, pain, and nausea/vomiting). Numbers of items were reduced from all scales save the pain scale.

Functional Assessment of Chronic Illness Therapy- Spiritual Well-Being Scale: (Cella et al. 2002; Cella and Nowinski 2002) has two subscales: one measuring sense of meaning and peace, and the other measuring the role of faith in illness, and total combined score assessing spiritual well-being. It is a psychometrically sound measure of spiritual well-being for individuals with cancer and with other chronic illnesses. Questions do not refer to specific religious beliefs or practices and are not biased for or against any particular religious group. The FACIT-Sp contains 12 items, and participants respond on a five-point scale (0 = not at all, 4 = very much).

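### The draft daily diary form does not carry the pain scale that Appendix A defines, and it adds a daily anxiety rating that no other part of the protocol mentions

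*Protocol*

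**What the plan says.** Pain is a secondary objective of the protocol, and Table 1 lists the Daily Pain Level Diary as an outcome. The Assessments and Measures section states: "Daily pain levels will be assessed via participant response on a visual analog scale". Appendix A describes the diary as covering pain alone ("This is a daily self-assessment of participant pain"). It is a 10-cm line from *no pain* to "worst pain possible", measured to the participant's mark and scored 0 to 10. Appendix A supports the choice by citing research that "visual analog pain scales are reliable and valid as both a sensitive measure of pain and as a measure of change in pain".

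Appendix B, introduced as a set of sample drafts, shows one diary page. It is headed VAAS and titled "Daily Diary of Pain and Anxiety". Its pain line runs from *No Pain* to *Much Pain*. Above that it asks "How Anxious did you Feel Today", with a line from *No Anxiety* to *Much Anxiety* and space for comments.

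The Data Analysis section uses the diary pain score directly: "In the case of pain levels measured by daily diary, the investigators will perform two repeated measures ANOVAs", comparing average baseline pain with the weeks after each session. A t-test is planned for pain on the day of the two-month follow-up against the average before psilocybin. For anxiety, the same section names HADS, HAM-A and STAI only.

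**The concern.** A visual analog score is defined by its end anchors. If the form and the definition name different upper ends, a mark at 10 has two meanings, and a reader of the results cannot tell which one applies. *Much Pain* is also not an extreme. A participant who already feels much pain may mark at or near the right-hand end and have little room left to record worsening. The Disease History section says that pain is very likely in Stage IV melanoma, so the upper part of the scale matters here.

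The anxiety line raises a different question. Anxiety is the trial's main construct, and seriously ill participants would be asked to rate it every day, yet the protocol gives this rating no purpose. How a diary item is summarised can be left to a statistical analysis plan. That the item is collected at all belongs in the protocol's list of measures and in its schedule.

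**Working it through.** The plan states no figure to reproduce on this point. The check is a comparison of the places that describe the diary.

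**Pain line**

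| Feature | Appendix A | Appendix B page |
|---|---|---|
| Construct | pain only | pain and anxiety |
| Lower anchor | no pain | No Pain |
| Upper anchor | worst pain possible | Much Pain |
| Length and scoring | 10 cm, scored 0 to 10 | line length cannot be judged from the extracted text |

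The lower anchors agree and the upper anchors do not. The anchor words on the form read cleanly, so this is not a fault of text extraction.

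**Where the pain score goes.** It enters the two ANOVAs and the two-month t-test. The two-month schedule and the Visit by Visit Description both call for the pain diary on that day. The Two-Month Follow-up section instead has the investigators administer a pain level measurement, without naming a form. If the two anchor wordings were used at different times, the t-test would compare different scales.

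**Daily anxiety line.** Each place where it could be declared was checked:

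- Study Objectives: not mentioned.
- Time and Events: rows for daily pain and daily medication diaries only.
- Assessments and Measures and Table 1: anxiety by HADS, STAI and HAM-A. The only daily data tied to anxiety are records of medication use.
- Screening and Baseline evaluation: participants are given pain and medication diaries.
- Data Analysis: no use.
- Appendix A: no entry.
- Appendix B contents list: a daily pain assessment, a pain diary and a medication diary, but no anxiety diary.

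Two entries come close. Adverse Event Collection gathers exacerbation of anxiety for seven days after each session, but does not name the diary as its source. The two-month schedule has a row labelled VAMS that is undefined and has no visit marked.

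**Amount collected.** The contents list assigns the pain diary to Visits 3 to 10, at approximate study days 0 and 43. Assuming that the combined page follows that span and that every day is completed, there are 43 − 0 = 43 daily anxiety ratings per participant, or 43 × 9 = 387 over nine completers.

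**The case against.** The strongest reply is that this is a draft form. Appendix B calls its contents sample drafts, and its list names both a daily pain assessment and a pain diary, while only one pain page is shown. The other might carry the Appendix A line. That stands: it cannot be said that participants will fill in the page shown. The page still contradicts Appendix A, and its draft status makes correction easy.

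The reply also limits what follows from the mismatch. A reader might infer that worsening pain cannot register. The documents give no distribution of pain scores, and participants may treat the right-hand end as simply the top of a line, so a ceiling is a risk and not a demonstrated loss. A reader might infer that comparability with the related pilot studies is broken. The protocol gives comparability as a reason for its choice of measures but does not state those studies' pain anchors.

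A further tempting inference is that valuable anxiety data are being discarded and should become a secondary outcome. Under first-order autocorrelation ρ, a seven-day mean has effective n = 7 / [1 + 2 Σ(1 − k/7)ρ^k], summed over k = 1 to 6, and cuts day-to-day error variance by 1 − 1/n. With assumed ρ of 0, 0.3 and 0.6, n is 7, 4.16 and 2.37, and the cuts are 86%, 76% and 58%. These figures concern a single item that the protocol neither describes nor validates. They say nothing about the precision of HADS and leave variation between persons untouched, which matters with six participants against three. HADS and STAI are already scheduled at Visits 3, 4, 5, 7, 8 and 10 and at two months, so the course of anxiety is not left unobserved. A baseline taken from the week before Visit 5 (day 14) would overlap the introductory psychotherapy at days 7 and 10. A new test at 0.05 would also add to a plan that makes no Bonferroni correction for its anxiety measures. A new anxiety outcome is therefore optional and not a correction that the plan needs.

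**Conclusion.** The point holds in two limited parts. First, the draft diary contradicts the pain scale that the protocol defines, so the top of the 0 to 10 score is not fixed for an outcome that enters three planned analyses (two ANOVAs and one t-test). Any ceiling is of unknown size. The mismatch applies equally to both arms, so it does not by itself bias the comparison between them. The primary outcome is unaffected. Second, the protocol collects a daily anxiety rating that it does not declare.

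This rests on the one diary page shown and on this protocol alone. A separate analysis plan could describe a use for the anxiety rating, but the protocol's own list of measures and schedule would still omit it. The point is worth correcting before the form is used, and it is modest in weight.

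**What to change.** Before use, print the diary with the Appendix A pain line: 10 cm, *no pain* to *worst pain possible*, scored 0 to 10. Use that same form at every time point, and say in the Two-Month Follow-up section that the pain rating there is taken on it. The diary is already planned for that day, so this only fixes the wording.

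For the daily anxiety line, choose one of two courses. Either add it to Table 1 and the schedule as an exploratory measure to be summarised descriptively, or remove it from the form.

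The cost is one reprinted page and a few lines of protocol text. Neither course adds to what participants are asked to do, and removing the anxiety line asks slightly less of them.
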